7.0 Protocol Treatment

7.1 Treatment Schedule

Cycle length: 28 days.

Agent	Route	Dose	Day	Retreatment
Lenalidomide	PO	25 mg*	1-21	Every 28 days
Pembrolizumab	IV	200mg	Every 21 days	Every 21 days
Dexamethasone	PO	40 mg	1, 8, 15, 22	Every 28 days

* If the patient has renal insufficiency, lenalidomide dose modifications should be made according to the following criteria:

CrCl >50 mL/min: No adjustment

CrCl 30-50 mL/min: 10 mg/day

CrCl <30 mL/min (no dialysis): 15 mg every 48 hours

CrCl <30 mL/min (dialysis): 5 mg daily (after HD (hemodialysis) on HD days)

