8.0 Dosage Modification Based on Adverse Events

Strictly follow the modifications in this table for the first **two** cycles, until individual treatment tolerance can be ascertained. Individual drugs can be dose reduced as per the table below depending on the adverse event attribution. Thereafter, these modifications should be regarded as guidelines to produce mild-to-moderate, but not debilitating, side effects. If multiple adverse events are seen, administer dose based on greatest reduction required for any single adverse event observed. Reductions apply to treatment given in the preceding cycle and are based on adverse events observed since the prior dose.

ALERT: ADR reporting may be required for some adverse events (See Section 10)

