8.1 Dose Levels for each drug in the combination

	Pembrolizumab (Every 21 days)	Lenalidomide (Days 1-21)	Dexamethasone (Days 1, 8, 15, 22)
Starting dose	200 mg	25 mg	40 mg
-1		15 mg	20 mg
-2		10 mg	12 mg
-3		5 mg	4 mg
-4		Discontinue	Discontinue

Note: If pembrolizumab is discontinued, the patient may continue treatment with the remaining drugs. If lenalidomide is discontinued, patient will go to event monitoring.

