8.11 Instruction for initiation of a new cycle of therapy

A new cycle of treatment may begin on the scheduled Day 1 of a new cycle if:

- The ANC is $\geq 1000/\mu\text{L}$
- The platelet count is $\geq 50,000/\mu\text{L}$
- Any other non-hematologic drug-related adverse event that may have occurred has resolved to \leq Grade 1 or baseline severity.

If these conditions are not met on Day 1 of a new cycle, dosing should be delayed for 1 week. At the end of that time, the patient should be re-evaluated to determine whether the criteria have been met. If the patient continues to fail to meet the above-cited criteria, delay therapy and continue to re-evaluate.

If any drug dosing was halted during the previous cycle and was restarted with a one-level dose reduction without requiring an interruption for the remainder of the cycle, then that reduced dose level will be initiated on Day 1 of the new cycle.

If any drug dosing was omitted for the remainder of the previous cycle or if the new cycle is held due to known hematologic toxicity newly encountered on the scheduled Day 1, then the new cycle will be started with a one-level dose reduction. If a new cycle of therapy cannot be restarted within 4 weeks of the scheduled Day 1 due to non-resolution of drug related toxicities, the patient will be removed from protocol therapy and will go to event monitoring.

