Respiratory, thoracic and mediastinal disorders	Pneumonitis	2	AE resolves to Grade 0-1	AE does not resolve within 12 weeks of last dose or inability to reduce corticosteroid to 10 mg or less of prednisone or equivalent per day within 12 weeks
		3-4	Permanently discontinue pembrolizumab	Permanently discontinue pembrolizumab
Renal and urinary disorders	Acute kidney injury or Chronic kidney disease (e.g. Renal failure or Nephritis)	2	AE resolves to Grade 0-1	AE does not resolve within 12 weeks of last dose or inability to reduce corticosteroid to 10 mg or less of prednisone or equivalent per day within 12 weeks
		3-4	Permanently discontinue pembrolizumab	Permanently discontinue pembrolizumab
	All Other Drug-Related Adverse Events ^b	3 or severe	AE resolves to Grade 0-1	AE does not resolve within 12 weeks of last dose or inability to reduce corticosteroid to 10 mg or less of prednisone or equivalent per day within 12 weeks
		4	Permanently discontinue pembrolizumab	Permanently discontinue pembrolizumab

Note: Permanently discontinue for any severe or Grade 3 (Grade 2 for pneumonitis) drug-related AE that recurs, or any lifethreatening event.

a If symptoms resolve within one hour of stopping drug infusion, the infusion may be restarted at 50% of the original infusion rate (e.g., from 100 mL/hr to 50 mL/hr). Otherwise dosing will be held until symptoms resolve and the subject should be premedicated for the next scheduled dose (Section 9.9f).

b Patients with intolerable or persistent Grade 2 drug-related AE may hold study medication at physician discretion. Permanently discontinue study drug for persistent Grade 2 adverse reactions for which treatment with study drug has been held, that do not recover to Grade 0-1 within 12 weeks of the last dose.

* Located at http://ctep.cancer.gov/protocolDevelopment/electronic_applications.ctc.htm

** Use the following to describe actions in the Action column:

- Omit = The current dose(s) for the specified drug(s) during a cycle is skipped. The patient does not make up the omitted dose(s) at a later time
- Hold/Delay = The current dose(s) of all drugs during a cycle is delayed. The patient does make up the delayed dose(s) when the patient meets the protocol criteria to restart drugs
- Discontinue = The specified drug(s) are totally stopped

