Nervous System Disorders	Peripheral sensory neuropathy Grade 3	Lenalidomide	Omit lenalidomide dose Follow at least weekly If the event resolves to \leq Grade 1 prior to Day 35, restart lenalidomide at next lower dose level and continue the cycle through Day 35	Omit lenalidomide for the remainder of the cycle. See Section 8.11 Instructions for Initiation of a New Cycle and reduce the dose of lenalidomide by 1 dose level
	Peripheral sensory neuropathy Grade 4	Lenalidomide	Discontinue lenalidomide	Discontinue lenalidomide
Immune system disorders	Allergic reaction Grade 2-3	Lenalidomide	Omit dose Follow at least weekly If the toxicity resolves to \leq Grade 1 prior to Day 35 restart at next lower dose level and continue the cycle until Day 35	Omit lenalidomide for the remainder of the cycle If the adverse event resolves to \leq Grade 1, reduce dose 1 level in next cycle If adverse event recurs, discontinue therapy
	Grade 4	Lenalidomide	Discontinue lenalidomide	Discontinue lenalidomide
Vascular disorders	Thromboembolic event \geq Grade 3	Lenalidomide	Omit dose and start anticoagulation; restart at investigator's discretion (maintain dose level)	Omit lenalidomide for remainder of cycle and start anticoagulation. Maintain dose level in next cycle
Kidney and Urinary System	Renal Insufficiency	Lenalidomide	CrCl $>$ 50 mL/min: No adjustment CrCl 30-50 mL/min: 10 mg/day CrCl $<$ 30 mL/min (no dialysis): 15 mg every 48 hours CrCl $<$ 30 mL/min (dialysis): 5 mg daily (after HD (hemodialysis) on HD days)	

CTCAE System/Organ/Class (SOC)	ADVERSE EVENT	AGENT	ACTION** Days 2-14 of cycle	ACTION** Day \geq 15 of cycle
Endocrine disorders	Hyperthyroidism or Hypothyroidism \geq Grade 2	Lenalidomide	Omit lenalidomide for remainder of cycle, evaluate etiology, and initiate appropriate therapy. See Instructions for Initiation of a New Cycle and reduce the dose of lenalidomide by 1 dose level	Omit lenalidomide for remainder of cycle, evaluate etiology, and initiate appropriate therapy. See Section 8.11 , Instructions for Initiation of a New Cycle and reduce the dose of lenalidomide by 1 dose level

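### Section 8.3: the stop for a recurrent Grade 2-3 allergic reaction to lenalidomide is missing from the Days 2-14 cell

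*Combined protocol and SAP*

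**What the plan says.** Section 8.3 gives separate lenalidomide instructions for adverse events on Days 2-14 and on Day 15 or later. For Allergic reaction Grade 2-3:

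- **Days 2-14:** omit the dose and follow the patient at least weekly. If the reaction has settled to Grade 1 or less in time, "restart at next lower dose level and continue the cycle until Day 35". Recurrence is not mentioned.
- **Day 15 or later:** omit lenalidomide for the rest of the cycle. If the reaction settles to Grade 1 or less, "reduce dose 1 level in next cycle If adverse event recurs, discontinue therapy".

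A Grade 4 allergic reaction stops lenalidomide in both columns.

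Four other provisions bear on the row:

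- Section 8.0 sets how binding it is: "Strictly follow the modifications in this table for the first" two cycles, and treat as guidance after that.
- Section 8.11 covers a drug restarted one level lower within a cycle: "then that reduced dose level will be initiated on Day 1 of the new cycle".
- Section 8.1 gives the lenalidomide dose levels as 25, 15, 10 and 5 mg, then discontinuation, and adds: "If lenalidomide is discontinued, patient will go to event monitoring".
- The Note under the Section 8.2 table has a general recurrence stop, "Permanently discontinue for any severe or Grade 3 (Grade 2 for pneumonitis) drug-related AE that recurs", but that table governs pembrolizumab.

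**The concern.** Allergic reaction is the only row of the 8.3 table with a recurrence stop. The sponsor evidently regards a repeat allergic reaction as different from a repeat rash, neuropathy or cytopenia, and allows one rechallenge. That decision appears in one column only, and nothing in the plan explains why the cycle day of the reaction should change it.

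What is at stake is patient safety. A patient whose first reaction was on Day 15 or later is stopped at the first recurrence. A patient who reacts twice on Days 2-14 is, on the written instruction, given the drug again. Lenalidomide is scheduled for Days 1-21 (Section 7.1), so the column without the stop covers 13 of the 21 scheduled dosing days and the column with it covers 7.

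**Working it through.** The plan states no figure to reproduce. The check is to trace the row through every timing of two reactions and then count restarts on the Section 8.1 ladder.

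**Step 1. Is there a recurrence rule elsewhere for lenalidomide?** Sections 8.0, 8.1 and 8.11 and the footnotes to 8.3 contain none. The 8.2 Note applies to pembrolizumab, and outside pneumonitis it starts at severe or Grade 3 events, so it would not reach a recurrent Grade 2 allergic reaction in any case.

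**Step 2. The timings.** Two windows for the first reaction and two for the repeat give 2 × 2 = 4 sequences.

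| First reaction | Repeat reaction | Stop stated? |
|---|---|---|
| Day ≥15 | Day ≥15 | Yes, Day ≥15 cell |
| Day ≥15 | Days 2-14 | Yes: the clause follows the next-cycle resumption and names no day |
| Days 2-14 | Day ≥15 | Yes: the repeat falls in the Day ≥15 cell and is a recurrence |
| Days 2-14 | Days 2-14 | No |

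One sequence of four has no stop. The second and third lines give the plan the benefit of a natural reading.

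**Step 3. Can the uncovered sequence arise while the table is binding?** Yes. A reaction on Days 2-14 of cycle 1 at 25 mg leads to a restart at 15 mg. Section 8.11 carries 15 mg into Day 1 of cycle 2. A repeat on Days 2-14 of cycle 2 falls in the same cell and leads to a restart at 10 mg. Both events fall in the two strict cycles.

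**Step 4. Number of restarts, both reactions always on Days 2-14.**

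- From 25 mg, as written: 25 → 15 → 10 → 5 → discontinue, so at most 3 restarts. The first follows the first reaction, so 3 − 1 = 2 follow a recurrence.
- From 25 mg, with the Day ≥15 rule: 1 restart, and 1 − 1 = 0 after a recurrence.
- In the two strict cycles, with one reaction per cycle: 2 restarts as written against 1 under the Day ≥15 rule, a difference of 1 re-exposure.
- From the reduced renal starting dose ("CrCl 30-50 mL/min: 10 mg/day"): 10 → 5 → discontinue, so 1 restart and 0 after a recurrence under either reading. The gap therefore concerns patients who start at 25 mg.

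**Step 5. How many patients?** No rate is given for Grade 2-3 allergic reaction. The nearest figure is in Section 15.27, which lists hypersensitivity with lenalidomide among uncommon events (<1%), in a list limited to important or life-threatening ones. If 1% is assumed for a first reaction, the maximum of 41 patients gives 41 × 0.01 = 0.41 patients. Each further percentage point adds another 0.41. Only those who also have a repeat reaction in the same window meet the gap.

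**The case against.** The strongest opposing case is that the gap is narrow and already hedged.

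- **Rarity.** On the assumed 1%, fewer than one patient would have even a first reaction. This stands as a statement about frequency, with the caution that the source figure covers only important or life-threatening events and Grade 2 reactions may be commoner.
- **Unequal sequences.** After a reaction late in the Days 2-14 window, weekly follow-up may put the restart at Day 15 or later, and a prompt recurrence then meets the stop. To reach the gap a patient must react twice by Day 14 of one cycle, or tolerate the rest of that cycle and react early in a later one. This stands: one in four is a count of timings, not a probability.
- **Evident intent.** The recurrence sentence names no day, and a clinician reading the whole row may infer a stop throughout. That is plausible, but the Days 2-14 cell gives its own complete instruction, and that instruction is to restart.
- **Ceiling.** A third restart needs three such reactions and, unless several fall in one cycle, comes after cycle 2, when the table is only guidance. This stands. The binding-period case is one extra re-exposure.
- **Safeguards.** Each restart requires resolution to Grade 1 or less and a lower dose, Grade 4 stops the drug, and Section 13.6 lets the investigator withdraw a patient for an adverse event. These limit harm. They are not a rule for recurrent Grade 2-3 reactions, and in cycles 1-2 the written rule points the other way. The end of the dose ladder is also not absolute, because the note closing Section 8.4 lets the Principal Investigator keep a patient on study beyond three reductions.

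**Conclusion.** The concern holds. For a first and a repeat Grade 2-3 allergic reaction that both fall on Days 2-14, the plan states no stop, and its literal instruction is to give lenalidomide again. In the binding two cycles, with one reaction per cycle, this means one extra re-exposure, at 10 mg, for a patient who started at 25 mg. The ceiling over the whole treatment is two restarts after a recurrence, against none under the plan's own Day ≥15 rule.

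This assumes that the recurrence sentence belongs to the Day ≥15 cell alone, as the table text shows, and that the Day ≥15 clause covers any sequence with an event in that window. The number of patients affected cannot be worked out from the documents and is likely to be small. The case for acting rests on the possible seriousness of a repeat allergic reaction and on the instruction being mandatory early in treatment. The primary endpoint definition, sample size, decision rule and error rates are unaffected.

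**What to change.** Put the same sentence in both cells of the row, replacing the existing recurrence sentence in the Day ≥15 cell: *If a Grade 2-3 allergic reaction recurs after restart, on any cycle day, discontinue lenalidomide.*

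This extends the sponsor's own rule to the whole row and names the drug to be stopped, where the current wording refers only to therapy. The Section 8.1 Note already says what follows, namely event monitoring.

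The cost is one sentence in two cells at the next amendment, with no added visits, tests or patients. The downside is that a few patients may leave lenalidomide, and so protocol treatment, earlier. The sponsor already accepts that consequence for reactions on Day 15 or later.

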8.4 Dose modifications for dexamethasone based on adverse events during a cycle

→ → Use the NCI Common Terminology Criteria for Adverse Events (CTCAE) version 4.0* unless otherwise specified ← ←

CTCAE System/Organ/Class (SOC)	ADVERSE EVENT	AGENT	ACTION**
Gastrointestinal disorders	Dyspepsia, gastric or duodenal ulcer, gastritis Grade 1-2 (Symptomatic; altered GI function; medical intervention indicated; limiting instrumental ADL)	Dexamethasone	Treat with H2 blockers, sucralfate, or omeprazole. If symptoms persist despite above measures, decrease dexamethasone dose by 1 dose level.
	Dyspepsia, gastric or duodenal ulcer, gastritis ≥Grade 3 (Severely altered GI function; TPN indicated; elective operative or endoscopic intervention indicated; limiting self care ADL; disabling)	Dexamethasone	Omit dexamethasone until symptoms adequately controlled. Restart one dose level below along with concurrent therapy with H2 blockers, sucralfate, or omeprazole. If symptoms persist despite above measures, discontinue dexamethasone and do not resume.
	Pancreatitis ≥Grade 3 (Severe pain; vomiting; medical intervention indicated (e.g., analgesia, nutritional support))	Dexamethasone	Discontinue dexamethasone and do not resume.
General disorders and administration site conditions	Edema ≥Grade 3 (limiting function and unresponsive to therapy or anasarca)	Dexamethasone	Diuretics as needed, and decrease dexamethasone dose by 1 dose level; if edema persists despite above measures, decrease dose another dose level. Discontinue dexamethasone and do not resume if symptoms persist despite second reduction.
Psychiatric disorders	Confusion or Mood alteration ≥Grade 2 (Severe disorientation; limiting self-care ADL)	Dexamethasone	Omit dexamethasone until symptoms resolve. Restart with one dose level reduction. If symptoms persist despite above measures, discontinue dexamethasone and do not resume.
Musculoskeletal and connective tissue disorders	Muscle weakness ≥Grade 2 Weakness limiting self care ADL; disabling	Dexamethasone	Decrease dexamethasone dose by one dose level; if weakness persists despite above measures decrease dose by one additional dose level. Discontinue dexamethasone and do not resume if symptoms continue to persist.

CTCAE System/Organ/Class (SOC)	ADVERSE EVENT	AGENT	ACTION**
Metabolism and nutrition disorders	Hyperglycemia \geq Grade 3 (>250 - 500 mg/dL; >13.9 - 27.8 mmol/L); hospitalization indicated	Dexamethasone	Treatment with insulin or oral hypoglycemics as needed. If uncontrolled despite above measures, decrease dose by one dose level at a time until levels are satisfactory.

* Located at http://ctep.cancer.gov/protocolDevelopment/electronic_applications.ctc.htm

** Use the following to describe actions in the Action column:

- Omit = The current dose(s) for the specified drug(s) during a cycle is skipped. The patient does not make up the omitted dose(s) at a later time
- Hold/Delay = The current dose(s) of all drugs during a cycle is delayed. The patient does make up the delayed dose(s) when the patient meets the protocol criteria to restart drugs
- Discontinue = The specified drug(s) are totally stopped

NOTE: Adverse events requiring a dose-reduction step for any or all drugs beyond the three dose-reduction steps (levels -1, -2 and -3) will be at the discretion of the Principal Investigator, if the decision is made for the patient to be kept on study. These dose reductions must be clearly recorded in reported clinical data.

9.0 Ancillary Treatment/Supportive Care

9.1 Full Supportive Care

Patients should receive full supportive care while on this study. This includes blood product support, antibiotic treatment, and treatment of other newly diagnosed or concurrent medical conditions. All blood products and concomitant medications such as antidiarrheals, analgesics, and/or antiemetics received from the first day of study treatment administration until 30 days after the final dose will be recorded in the medical records.

9.2 Thromboprophylaxis

All patients should receive aspirin 325 mg daily for thromboprophylaxis. For patients considered high risk for thrombosis, therapeutic anticoagulation with warfarin or low molecular weight heparin should be used

9.3 Steroid use

Patients may continue on low level/stable steroid doses for replacement or inhalation therapy.

9.4 Medications not permitted

The following medications are not permitted during the trial:

- Any other investigational treatment
- Any other systemic anti-neoplastic therapy including, but not limited to, immunotherapy, hormonal therapy or monoclonal antibody therapy
- Any external beam radiotherapy

9.5 Use of growth factors

Blood products and growth factors should be utilized as clinically warranted and following institutional policies and recommendations. The use of growth factors should follow published guidelines of the Journal of Clinical Oncology, Vol 24, No 18 (June 20), 2006: pp. 2932-2947.

9.6 Bisphosphonates

Patients may receive concurrent treatment with a bisphosphonate.

9.7 Pneumonitis:

For **Grade 2 events**, treat with systemic corticosteroids. When symptoms improve to Grade 1 or less, steroid taper should be started and continued over no less than 4 weeks. For **Grade 3-4 events**, immediately treat with intravenous steroids. Administer additional anti-inflammatory measures, as needed.

Add prophylactic antibiotics for opportunistic infections in the case of prolonged steroid administration.

9.8 Diarrhea/Colitis

Subjects should be carefully monitored for signs and symptoms of enterocolitis (such as diarrhea, abdominal pain, blood or mucus in stool, with or without fever) and of bowel perforation (such as peritoneal signs and ileus).

- All subjects who experience diarrhea/colitis should be advised to drink liberal **quantities of clear fluids. If sufficient oral fluid intake is not feasible, fluid and**

electrolytes should be substituted via IV infusion. For Grade 2 or higher diarrhea, consider GI consultation and endoscopy to confirm or rule out colitis.

- For **Grade 2 diarrhea/colitis** that persists greater than 3 days, administer oral corticosteroids.
- For **Grade 3 or 4 diarrhea/colitis** that persists > 1 week, treat with intravenous steroids followed by high dose oral steroids.
- When symptoms improve to Grade 1 or less, steroid taper should be started and continued over no less than 4 weeks.

9.9a Type 1 diabetes mellitus

If new onset, including diabetic ketoacidosis [DKA] or \geq Grade 3 Hyperglycemia, if associated with ketosis (ketonuria) or metabolic acidosis (DKA)

- For **T1DM** or **Grade 3-4** Hyperglycemia
- Insulin replacement therapy is recommended for Type I diabetes mellitus and for Grade 3-4 hyperglycemia associated with metabolic acidosis or ketonuria.
- Evaluate patients with serum glucose and a metabolic panel, urine ketones, glycosylated hemoglobin, and C-peptide.

9.9b Hypophysitis:

- For **Grade 2** events, treat with corticosteroids. When symptoms improve to Grade 1 or less, steroid taper should be started and continued over no less than 4 weeks. Replacement of appropriate hormones may be required as the steroid dose is tapered.
- For **Grade 3-4** events, treat with an initial dose of IV corticosteroids followed by oral corticosteroids. When symptoms improve to Grade 1 or less, steroid taper should be started and continued over no less than 4 weeks. Replacement of appropriate hormones may be required as the steroid dose is tapered.

9.9c Hyperthyroidism or Hypothyroidism:

Thyroid disorders can occur at any time during treatment. Monitor patients for changes in thyroid function (at the start of treatment, periodically during treatment, and as indicated based on clinical evaluation) and for clinical signs and symptoms of thyroid disorders.

- **Grade 2** hyperthyroidism events (and **Grade 2-4** hypothyroidism):
 - In hyperthyroidism, non-selective beta-blockers (e.g. propranolol) are suggested as initial therapy
 - In hypothyroidism, thyroid hormone replacement therapy, with levothyroxine or liothyronine, is indicated per standard of care
- **Grade 3-4** hyperthyroidism
 - Treat with an initial dose of IV corticosteroid followed by oral corticosteroids. When symptoms improve to Grade 1 or less, steroid taper should be started and continued over no less than 4 weeks. Replacement of appropriate hormones may be required as the steroid dose is tapered.

9.9d Hepatic:

- For **Grade 2** events, monitor liver function tests more frequently until returned to baseline values (consider weekly).
 - Treat with IV or oral corticosteroids
- For **Grade 3-4** events, treat with intravenous corticosteroids for 24 to 48 hours.
- When symptoms improve to Grade 1 or less, a steroid taper should be started and continued over no less than 4 weeks.

9.9e Renal Failure or Nephritis:

- For **Grade 2** events, treat with corticosteroids.
- For **Grade 3-4** events, treat with systemic corticosteroids.
- When symptoms improve to Grade 1 or less, steroid taper should be started and continued over no less than 4 weeks.

9.9f Management of Infusion Reactions:

Signs and symptoms usually develop during or shortly after drug infusion and generally resolve completely within 24 hours of completion of infusion.

Table 9.9e1 below shows treatment guidelines for subjects who experience an infusion reaction associated with administration of pembrolizumab (MK-3475).

Table 9.9e1 Infusion Reaction Treatment Guidelines

NCI CTCAE Grade	Treatment	Premedication at subsequent dosing
Grade 1 Mild reaction; infusion interruption not indicated; intervention not indicated	Increase monitoring of vital signs as medically indicated until the subject is deemed medically stable in the opinion of the investigator	None
Grade 2 Requires infusion interruption but responds promptly to symptomatic treatment (e.g., antihistamines, NSAIDS, narcotics, IV fluids); prophylactic medications indicated for <=24 hrs	
Stop Infusion and monitor symptoms. Additional appropriate medical therapy may include but is not limited to: IV fluids Antihistamines NSAIDS Acetaminophen Narcotics
 
Increase monitoring of vital signs as medically indicated until the subject is deemed medically stable in the opinion of the investigator. If symptoms resolve within one hour of stopping drug infusion, the infusion may be restarted at 50% of the original infusion rate (e.g., from 100 mL/hr to 50 mL/hr). Otherwise dosing will be held until symptoms resolve and the subject should be premedicated for the next scheduled dose.
 
Subjects who develop Grade 2 toxicity despite adequate premedication should be permanently discontinued from further trial treatment administration.
	
Subject may be premedicated 1.5h (\pm 30 minutes) prior to infusion of pembrolizumab (MK-3475) with:
 
Diphenhydramine 50 mg po (or equivalent dose of antihistamine)
 
Acetaminophen 500-1000 mg po (or equivalent dose of antipyretic)

NCI CTCAE Grade	Treatment	Premedication at subsequent dosing

Grades 3 or 4
 
Grade 3: Prolonged (i.e., not rapidly responsive to symptomatic medication and/or brief interruption of infusion); recurrence of symptoms following initial improvement; hospitalization indicated for other clinical sequelae (e.g., renal impairment, pulmonary infiltrates)
 
Grade 4: Life-threatening; pressor or ventilatory support indicated
	
Stop Infusion.
 
Additional appropriate medical therapy may include but is not limited to:
 
 IV fluids Antihistamines NSAIDS Acetaminophen Narcotics Oxygen Pressors Corticosteroids Epinephrine 
Increase monitoring of vital signs as medically indicated until the subject is deemed medically stable in the opinion of the investigator. Hospitalization may be indicated.
 
Subject is permanently discontinued from further trial treatment administration.
	
No subsequent dosing

Appropriate resuscitation equipment should be available in the room and a physician readily available during the period of drug administration.
		

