10.55 Events of Clinical Interest

Selected non-serious and serious adverse events are also known as Events of Clinical Interest (ECI) and must be recorded as such on the Adverse Event case report forms/worksheets and reported within 24 hours to the Sponsor and within 2 working days to Merck Global Safety. (Attn: Worldwide Product Safety; [REDACTED])

Events of clinical interest for this trial include:

1. An overdose of Merck product, as defined above - Definition of an Overdose for This Protocol and Reporting of Overdose to the Sponsor, that is not associated with clinical symptoms or abnormal laboratory results.
2. An elevated AST or ALT lab value that is greater than or equal to 3X the upper limit of normal and an elevated total bilirubin lab value that is greater than or equal to 2X the upper limit of normal and, at the same time, an alkaline

phosphatase lab value that is less than 2X the upper limit of normal, as determined by way of protocol-specified laboratory testing or unscheduled laboratory testing.*

*Note: These criteria are based upon available regulatory guidance documents. The purpose of the criteria is to specify a threshold of abnormal hepatic tests that may require an additional evaluation for an underlying etiology. The trial site guidance for assessment and follow up of these criteria can be found in the Investigator Trial File Binder (or equivalent).

10.56 Additional adverse events:

A separate guidance document has been provided entitled “Event of Clinical Interest Guidance Document” (previously entitled, “Event of Clinical Interest and Immune-Related Adverse Event Guidance Document”). This document can be found in Appendix 4 and provides guidance regarding identification, evaluation and management of ECIs and irAEs.

ECIs (both non-serious and serious adverse events) identified in this guidance document from the date of first dose through 90 days following cessation of treatment, or 30 days after the initiation of a new anticancer therapy, whichever is earlier, need to be reported within 24 hours to the Sponsor and within 2 working days to Merck Global Safety. (Attn: Worldwide Product Safety; [REDACTED]), regardless of attribution to study treatment, consistent with standard SAE reporting guidelines.

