- 15.191 Pembrolizumab side effects vary greatly from those of traditional chemotherapy and can vary in severity from mild to life threatening. Instruct patients to report any side effects to the study team immediately. Side effects may be immediate or delayed up to months after discontinuation of therapy. Most side effects are reversible with prompt intervention of corticosteroids.
- 15.192 Diarrhea can be seen however is less common than that seen with anti-CTLA-4 agents. However it can be severe, leading to colonic perforation. Instruct patients to report ANY increase in the number of stools and/or change in baseline, blood in the stool, abdominal pain to the study team immediately.
- 15.193 Rash/pruiritis/dermatitis is seen. Patients should report any rash to the study team. Treat per [Section 9.0](#) and monitor for effectiveness.

- 15.194 Monitor LFT's closely as elevations in these levels could indicate early onset autoimmune hepatitis. Patients should also be instructed to report any jaundice, or right upper quadrant pain to the study team immediately.
 - 15.195 Pneumonitis can be seen and may be mild (only seen on imaging) to severe. Patients should be instructed to report any SOB, dyspnea, cough, chest pain, etc. to the study team immediately. Patients reporting these symptoms should have a pulse ox checked and consider immediate imaging per the treating MD.
 - 15.196 Endocrinopathies (including hypopituitarism, hypothyroidism, hypophysitis, and adrenal insufficiency) are seen with this agent. Patients may present only with the vague sense of fatigue and "not feeling well". Additional symptoms may be that of nausea, sweating and decreased activity tolerance. Instruct patients to report these signs or symptoms immediately and obtain appropriate labs as ordered by MD.
 - 15.197 Patients who are started on steroid therapy for any side effects of pembrolizumab toxicity should be instructed to take the steroids as ordered, and not to discontinue abruptly as symptoms may return and be severe. Patients may be on steroid therapy for weeks. Instruct patients to report any increase or change in side effects with any dosage decrease as patients may need a slower taper.
 - 15.198 Fatigue is common and may or may not be associated with immune related side effects. Assess patient's fatigue level prior to each cycle of therapy and report any *changes to the study team*.

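### Section 9.8 starts steroids later for Grade 3-4 diarrhea/colitis (after more than 1 week) than for Grade 2 (after more than 3 days)

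*Combined protocol and SAP*

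**What the plan says.** Section 9.8 gives two consecutive steroid instructions for diarrhea/colitis:

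- Grade 2 "that persists greater than 3 days, administer oral corticosteroids".
- Grade 3 or 4 "that persists > 1 week, treat with intravenous steroids followed by high dose oral steroids".

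The section also asks for monitoring for enterocolitis and perforation, for oral or intravenous fluids, and, from Grade 2 upwards, for GI consultation and endoscopy to be considered. Section 8.2 has pembrolizumab omitted at Grade 2-3 and permanently stopped at Grade 4, but does not say when steroids begin. The available text contains no other steroid instruction for Grade 3-4 diarrhea/colitis.

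Two nursing guidelines for pembrolizumab bear on timing. Section 15.191 states: "Most side effects are reversible with prompt intervention of corticosteroids". Section 15.192 says of diarrhea: "However it can be severe, leading to colonic perforation". Section 10.56 refers to a guidance document in Appendix 4 that "provides guidance regarding identification, evaluation and management of ECIs and irAEs"; that appendix is not in the text available for review.

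**The concern.** The strength of treatment rises with grade, from oral to intravenous steroids, but the start moves later. Read literally, the sicker patient is told to wait longer. A wait before steroids in diarrhea can be defended, because other causes may need to be ruled out. It is hard to defend a wait that lengthens as the event becomes more severe, when the protocol itself names perforation as a possible outcome.

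Section 9.8 is also silent on an event that worsens from Grade 2 to Grade 3. It does not say whether the day count carries on or starts again, or whether a Grade 2 trigger already met still applies.

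The event is foreseeable. Section 15.17 lists diarrhea at more than 10% and colitis at 1% to 10% with pembrolizumab, and 15.27 lists diarrhea as very common with lenalidomide. What is at stake is patient safety, not the primary analysis.

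**Working it through.** The plan states no figure to reproduce. The check compares the two thresholds and then sets 9.8 beside the other toxicity sections.

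**Gap between the thresholds.** Take onset as day 1.

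- Grade 2, more than 3 days: first met on day 4.
- Grade 3-4, more than 1 week: first met on day 8.
- Days with a Grade 2 instruction but no Grade 3-4 instruction: 4, 5, 6 and 7, so 8 − 4 = 4 days.

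A different day-counting convention moves both dates equally, so the gap stays at 7 − 3 = 4 days.

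**Worsening event.** Suppose the event is Grade 2 on days 1 to 3 and Grade 3 from day 4.

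- Count from onset: intravenous steroids are first instructed on day 8.
- Count restarted at Grade 3: 4 + 7 = day 11.

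Had the same event stayed at Grade 2, oral steroids would have been instructed on day 4.

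**Comparison with the other sections that use steroids at Grade 3-4.**

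| Section | Toxicity | Grade 2 | Grade 3-4 |
|---|---|---|---|
| 9.7 | Pneumonitis | Steroids, no stated wait | "immediately treat with intravenous steroids" |
| 9.8 | Diarrhea/colitis | Oral steroids after more than 3 days | Intravenous steroids after more than 1 week |
| 9.9b | Hypophysitis | Steroids, no stated wait | "treat with an initial dose of IV corticosteroids followed by oral corticosteroids"; no stated wait |
| 9.9c | Hyperthyroidism | Beta-blocker suggested, no steroid | Intravenous then oral steroids, no stated wait |
| 9.9d | Hepatic | Steroids, no stated wait | "treat with intravenous corticosteroids for 24 to 48 hours"; no stated wait |
| 9.9e | Renal | Steroids, no stated wait | Steroids, no stated wait |

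All five comparison sections state no wait at Grade 3-4, and in none does a higher grade mean later steroids. Section 9.8 is the only one where it does.

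The documents give no rate for Grade 3-4 diarrhea/colitis lasting 4 to 7 days, so the number of patients affected cannot be estimated.

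**The case against.** The strongest objection is that the governing guidance may lie elsewhere. Appendix 4 covers management of immune-related events and may call for earlier steroids, and 9.8 does not prohibit them. This limits what can be said about actual care, but it does not rescue 9.8. If Appendix 4 starts steroids earlier, the protocol conflicts with its own guidance; if it uses the same times, the inversion stands. Section 9.8 does not refer the reader to Appendix 4.

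Patients are also not unmanaged on days 4 to 7. Pembrolizumab is omitted or stopped (8.2), lenalidomide is omitted for other non-hematologic toxicity of Grade 3 or higher (8.3), supportive care is given (9.1), and bowel symptoms must be reported at once (15.192). Dexamethasone 40 mg is scheduled weekly (7.1), so unless it has been reduced or omitted one dose falls in any 7-day window. All this is true, but none of it starts steroids for colitis. The weekly dexamethasone is myeloma treatment and is scheduled for Grade 2 patients too, so it cannot explain the difference between grades.

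A third argument is that a fuller work-up may be wanted before intravenous and high-dose steroids. The documents do not give that reason, and 9.8 offers the same advice on consultation and endoscopy for every grade from 2 upwards.

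Two points on the other side stand. Only 9.7 says that treatment is immediate; the other four comparison sections simply give no timing. And the day-11 result depends on a restarted count, which 9.8 does not state; a count from onset is the more natural reading.

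**Conclusion.** The concern holds. As written, 9.8 places the steroid trigger for Grade 3-4 diarrhea/colitis four days later than the trigger for Grade 2. That runs against the pattern of the five comparable sections and the protocol's own emphasis on prompt corticosteroids.

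Confidence is high for the wording defect, which rests only on the two thresholds in 9.8. It is lower for the effect on patients, because clinicians may treat earlier and Appendix 4 could not be checked. The missing rule for worsening events is a lesser gap and would not by itself carry the point. The primary endpoint, sample size and error rates are not affected.

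**What to change.** Reword the Grade 3-4 bullet in 9.8 so that its wait is no longer than the Grade 2 wait. Having no fixed wait would match 9.7. State that an event worsening from Grade 2 to Grade 3 keeps its original start day and does not lose a steroid trigger already met. Then check the new wording against Appendix 4 and align the two. The exact timing is for the investigator, the sponsor and the drug supplier to set.

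The cost is a wording change to two bullets and one cross-check, with no added visits or tests.
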